6.7.2.2. Overall Response

Analyses similar to those for CR rate will be performed for overall response rate CR+CRi. In addition, number and percent of subjects whose best tumor response are morphologic leukemia-free state (MLFS), partial response (PR), stable disease (SD), or treatment failure (TF) will also be provided.

6.7.2.3. CR plus MRD-Negative CRi

Analyses similar to those for CR rate will be performed for CR plus MRD-negative CRi rate.

6.7.2.4. Time to Response

Time to response is defined as the time from randomization to achieving a best response of CR or CRi for subjects who achieved a response. Descriptive statistics will be summarized by treatment arm using the Kaplan-Meier method (with no censored observations). Time to best response of CR and time to CR plus MRD-negative CRi are similarly defined and will be summarized, respectively.

6.7.2.5. Duration of Response

Duration of response is defined for subjects who achieved a best response of CR or CRi as the time from achieving CR or CRi to relapse. Duration will be censored at the time of last tumor assessment for subjects who did not relapse. Duration of response will be summarized descriptively using the Kaplan-Meier method. Duration of response for best response of CR and best response of CR plus MRD-negative CRi are similarly defined and will be summarized, respectively.

6.7.2.6. Minimal Residual Disease

The following analyses will be performed for MRD by treatment arm:

- For subjects who achieve CR, CRi, or MLFS, respectively, number and percent of subjects who achieve MRD negativity at time of achieving the response or at any time during the response
- For all subjects of the ITT population, number and percent of subjects who achieve MRD negativity at the time of achieving CR or CRi, or at any time during CR or CRi. Subjects who do not achieve CR or CRi will be considered MRD positive in these analyses. Analyses similar to those for CR rate will be performed.

6.7.2.7. Patient-Reported Outcomes

Descriptive statistics (number of observations, mean, standard deviation, median, minimum, maximum) at baseline and each post-baseline time point will be reported by treatment group for each of the 9 PRO measures, including FACT-Leu subscale scores (PWB, SWB, EWB, FWB, and LeuS), FACT-Leu summary scores (TOI and FACT-Leu total score), EQ-5D-5L index score, and VAS.

To compute each of the FACT-Leu subscale scores (PWB, SWB, EWB, FWB, and LeuS), there must be >50% non-missing items; otherwise the respective subscale score is considered missing, and the summary scores (TOI and FACT-Leu total score) containing the missing subscale score are also considered missing.

Compliance rates, defined as the percent of the number of questionnaires received relative to the number expected per protocol-specified collection schedule, will be assessed by treatment group. Reasons for non-compliance will be explored.

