Medical resource utilization	Information on all health care needs during treatment (eg, physiotherapist) to be collected	Continuous from the time of signing of the ICF until 30 days after the last dose of study drug			
Patient-reported outcomes					
FACT-Leu	PROs should be performed on Day 1 of each cycle before dosing and before any study tests or procedures are conducted.		X	X	Only at first FU
EQ-5D-5L			X	X	Only at first FU
Laboratory Assessments					
Hematology	At least the following parameters (hemoglobin, platelet count, absolute WBC count, absolute monocyte count, absolute basophil count, absolute eosinophil count, absolute neutrophil count, absolute lymphocyte count, and peripheral blast count) must be assessed within 3 days of the indicated days of each cycle and results reviewed prior to starting dosing if applicable.	X	Days 1, 8, and 22	X	
Coagulation panel	aPTT, INR or prothrombin time (PT) must be assessed at screening and as clinically indicated afterward	X			
Clinical chemistry	At least the following parameters (AST, ALT, sodium, potassium, magnesium, BUN, phosphate, uric acid, calcium, alkaline phosphatase, creatinine, total bilirubin) must be assessed within 3 days of Day 1 of each cycle and results reviewed prior to starting the cycle.	X	X	X	
Assessment for active hepatitis or history of HIV		X			
Serum β -hCG or urine pregnancy test	For women of childbearing potential only	X	Only if clinically indicated		

Procedure (Part B)	Notes	Screening Phase	Open-Label Treatment Phase		Follow-up Phase
		Within 28 days before randomization	Day 1 of each cycle (± 48 hours) unless otherwise indicated (each cycle = 28 days)	EOT	Every 3 months (±7 days)
Disease Evaluations: A +/- 7-day window exists for completion of disease evaluation visits. Refer to Section 9.2 for details on efficacy evaluations					

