2. OBJECTIVES, ENDPOINTS, AND HYPOTHESIS

2.1. Objectives and Endpoints

2.1.1. Objectives

Primary Objectives

Part A: to assess the safety of talacotuzumab monotherapy and confirm the RP2D in subjects with AML for whom experimental therapy is appropriate (as assessed by their treating physician).

Part B: The primary objectives of the study are to assess CR rate and OS in subjects with previously untreated AML who are not eligible for intense induction chemotherapy and who are randomly assigned to receive decitabine plus talacotuzumab at the RP2D or decitabine alone.

Secondary Objectives (Part B)

The secondary objectives are:

- To assess EFS;
- To determine the overall response rate (ORR) defined as rate of complete response (CR) and complete response with incomplete blood count recovery (CRi);
- To determine the rate of CR plus MRD negative CRi
- To assess the relapse-free survival (RFS);
- To assess time to response and duration of response for subjects who achieve CR/CRi;
- To assess minimal residual disease (MRD);
- To assess the safety profile of talacotuzumab in combination with decitabine;
- To assess the pharmacokinetics of talacotuzumab and decitabine alone and in combination;
- To assess the immunogenicity talacotuzumab alone (Part A) and in combination with decitabine (Part B);
- To assess patient-reported outcomes (PROs) using the FACT-Leu and EQ-5D-5L.

Exploratory Objectives

The exploratory objectives are:

- To explore PK/PD relationships of talacotuzumab through analysis of talacotuzumab PK, biomarkers, PD markers, and clinical end points;
- To explore biomarkers predictive of clinical response;
- To collect medical resource utilization (MRU) data that may be used in future economic modeling (the construction and reporting of the economic model will be conducted separately from this study).

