11.10. Patient-reported Outcomes and Medical Resource Utilization

FACT-Leu and EQ-5D-5L scores will be summarized at each time point. Medical resource utilization will be descriptively summarized by treatment group. Duration of hospitalization (total days length of stay, including duration by wards; eg, intensive care unit), frequencies of outpatient medical encounters and treatments will be calculated and tabulated.

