2.2. Secondary and Exploratory Endpoints (Part B)

Secondary endpoints to be summarized in the clinical study report include the following:

- Event-free survival (EFS), defined as the time from randomization to treatment failure, relapse from CR or CR with incomplete blood count recovery (CRi), or death from any cause, whichever occurs first. Treatment failure is defined as >25% absolute increase in the bone marrow blast count from baseline to the present assessment.
- Overall response rate (ORR, CR + CRi)
- Rate of CR plus minimal residual disease (MRD) negative CRi
- Time to response, defined for subjects who achieved a best response of CR or CRi as time from randomization to achieving the best response
- Duration of response, defined for subjects who achieved a best response of CR or CRi as time from achieving CR or CRi to relapse
- MRD negativity
- Patient-reported outcomes (PROs) using the FACT-Leu (FACT-Leu Subscale, Trial Outcome Index, Physical Function, Functional Well-being, FACT-Leu Total Score, Emotional Well-being, Social/Family Function) and EQ-5D-5L (index score and Visual Analogue Scale [VAS] score).
- Safety

Transfusion frequency will be an exploratory endpoint to be summarized in the clinical study report.

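### PRO scores are planned only as raw visit means by arm, with no within-subject change or longitudinal model, so change in quality of life can be confused with change in who is still being measured

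*SAP*

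**What the plan says.** Protocol 2.1.1 makes PROs a secondary objective of Part B ("To assess patient-reported outcomes (PROs) using the FACT-Leu and EQ-5D-5L"), and SAP 2.2 lists them among the secondary endpoints ("Patient-reported outcomes (PROs) using the FACT-Leu").

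The planned analysis is short. Protocol 11.10 says "FACT-Leu and EQ-5D-5L scores will be summarized at each time point". SAP 6.7.2.7 specifies "Descriptive statistics (number of observations, mean, standard deviation, median, minimum, maximum") and says that these "at baseline and each post-baseline time point will be reported by treatment group for each of the 9 PRO measures". The nine measures are five FACT-Leu subscales, the TOI, the FACT-Leu total, the EQ-5D-5L index and the VAS.

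The same section sets a rule for missing items within a subscale. On missing questionnaires it plans "Compliance rates, defined as the percent of the number of questionnaires received relative to the number expected per protocol-specified collection schedule", by treatment group, and adds "Reasons for non-compliance will be explored".

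Neither document plans a PRO change from baseline, a repeated-measures model, an estimated difference between arms, or a rule for death and dropout. The same SAP does plan change from baseline for laboratory tests (6.8.2) and vital signs (6.8.4).

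Protocol Table 1B schedules both questionnaires on Day 1 of each cycle, at end of treatment, and in follow-up "Only at first FU". Table 1C, which applies during Amendment 6, has no PRO row.

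**The concern.** Treatment stops at treatment failure, relapse, unacceptable toxicity or death, and per-cycle questionnaires stop with it. The mean at a late cycle therefore describes only the randomized subjects who have lasted that long. A raw mean that rises from Cycle 1 to Cycle 7 could reflect subjects feeling better, or it could reflect frailer subjects having left. The planned table cannot tell these apart, because it never compares a subject with that subject's own baseline.

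The same applies between arms. If one arm loses subjects faster and the sicker ones go first, its later means are inflated more, and it can look better for that reason alone. No other comparison of PRO scores by arm is planned, so readers will use this table to compare arms on a stated secondary objective.

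**Working it through.** **1. The plan's own figure, used only as a source of expected attrition.** SAP section 4 assumes median EFS of 4.0 months (decitabine alone) and 6.8 months (combination), HR 0.59, with 90 events giving 80% power on a 90% CI.

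- Ratio of medians: 4.0 / 6.8 = 0.588.
- Schoenfeld power: Φ(√90 × |ln 0.59| / 2 − 1.645) = Φ(2.503 − 1.645) = Φ(0.858) = 0.80.

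The figure reproduces. The documents give no PRO effect size, power or sample size to check.

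**2. Who is left at each visit.** Assume exponential curves: share event-free = 0.5^(t / median), with t = (cycle − 1) × 28 / 30.4375 months. The share alive uses the plan's OS medians of 8.0 and 11.4 months.

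| Visit | t (months) | Event-free, decitabine alone | Event-free, combination | Alive, decitabine alone | Alive, combination |
|---|---|---|---|---|---|
| Cycle 4 Day 1 | 2.76 | 62% | 75% | 79% | 85% |
| Cycle 6 Day 1 | 4.60 | 45% | 63% | 67% | 76% |
| Cycle 7 Day 1 | 5.52 | 38% | 57% | 62% | 71% |
| Cycle 13 Day 1 | 11.04 | 15% | 32% | 38% | 51% |

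EFS stands in for time on treatment, which the documents do not give.

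**3. Size of the possible bias (illustration).** Each subject has a constant standard normal score, so there is no true change over time and no treatment effect. Time on treatment is exponential, with the hazard multiplied by h for each SD lower score, calibrated to marginal medians of 4.0 and 6.8 months. The multiplier h is an assumption; the documents give none. The mean score among those remaining, by numerical integration, is:

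| h | Month 6, 4.0-month arm | Month 6, 6.8-month arm | False gap, month 6 | False gap, month 9 |
|---|---|---|---|---|
| 1.0 | 0 | 0 | 0 | 0 |
| 1.3 | +0.26 SD | +0.16 SD | 0.10 SD | 0.15 SD |
| 1.5 | +0.38 SD | +0.24 SD | 0.14 SD | 0.19 SD |
| 1.8 | +0.50 SD | +0.33 SD | 0.17 SD | 0.22 SD |

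The true values are all zero. With the same median in both arms, the gap is zero for every h, because the two columns are then identical; the upward drift within each arm remains.

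**4. Does change from baseline cure it?** Two further simulations used 1,000,000 subjects per arm, with log-hazard falling by 0.25 to 0.75 per SD.

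- *Dropout depends on a stable underlying score* (within-subject correlation 0.7). Raw means at Cycle 7 are inflated by 0.19 to 0.46 SD in the faster arm and 0.12 to 0.31 SD in the other. Mean change from baseline is about 0, so here change scores do cure it.
- *Dropout depends on each subject's own slope* (assumed slope SD 0.1 SD per month). Change from baseline at Cycle 7 is itself inflated, by 0.13 to 0.30 SD and 0.08 to 0.21 SD. Here change scores alone are not enough.

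**5. Is there a usable baseline?** SAP 5.5 takes the last value up to the day of randomization. Table 1B has no screening PRO; the first is on Cycle 1 Day 1, and randomization is allowed up to 3 days before the first dose. Read literally, a subject randomized before the dosing day has no PRO baseline.

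**The case against.** **The bias is conditional.** The documents give no link between score and dropout. Without one the bias is zero, and true deterioration could mask any drift. This stands. A reader might infer that scores will falsely improve and that the arm losing subjects faster will look better; the documents support only that this can happen. Even so, the main exits are treatment failure, relapse, toxicity and death, so assuming no link at all is the less plausible choice.

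**The gap between arms rests on overtaken planning values.** SAP section 3 records that OS met the futility criterion, that recruitment ended and that talacotuzumab was stopped. That does not reveal time on treatment by arm, but it removes any ground for treating 4.0 versus 6.8 months as the expected difference in attrition. This stands, and with equal attrition the gap disappears.

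**The gap is small against noise.** With about 36% and 54% remaining at month 6, the standard error of the arm difference is √[1/(n × 0.36) + 1/(n × 0.54)] SD. That is 0.15 SD for n = 200 per arm and 0.24 SD for n = 80; actual enrolment is not stated. The central gap of 0.14 SD is below one standard error in both cases. Fair, but a systematic shift is still undesirable in a table meant for interpretation.

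**Attrition is already reported.** The number of observations per visit, compliance by arm and reasons for non-compliance are all planned. They make attrition visible but do not correct the means. Compliance is measured against questionnaires expected under the schedule. If subjects who have died or stopped no longer count as expected, which the SAP does not settle, compliance could be high with much of the cohort gone.

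**Later respondents are not different people.** It would be wrong to say that the Cycle 6 mean comes largely from subjects outside the baseline mean. Respondents are a subset of those randomized, and about 45% and 63% are still event-free at that visit. End-of-treatment and first follow-up questionnaires also reach subjects who have stopped.

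**Conclusion.** The point holds as a risk to interpretation. For a stated secondary endpoint, the plan gives raw summaries at each visit and nothing within subject, which is less than it gives vital signs. Visit means planned this way mix change in quality of life with change in who is measured.

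Under an assumed multiplier of 1.3 to 1.8 per SD and the planning EFS medians, the false gap at month 6 is 0.10 to 0.17 SD in favour of the arm losing subjects faster. Both conditions are needed: no link between score and dropout, or equal attrition, gives no gap. The drift within arms needs only the link.

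A reader might go further and infer damage to the trial's error control or main conclusions. The documents do not support that: PROs carry no hypothesis test, alpha or power.

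**What to change.** Amend SAP 6.7.2.7 as follows.

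- Define the PRO baseline as the Cycle 1 Day 1 assessment before dosing, as an exception to SAP 5.5.
- Report change from baseline at each visit beside the raw values, and keep the planned counts, compliance rates and reasons for non-compliance.
- Show mean profiles grouped by last on-treatment cycle, so that the dropout pattern is visible.
- Add a supportive mixed model for repeated measures on change from baseline, with treatment, visit, treatment by visit, baseline score and the two randomization factors (ECOG status and type of AML), giving differences between arms with 95% CIs.
- State the limits: the model assumes that dropout depends on observed scores; it implicitly extrapolates past death, so it is not an estimate for subjects while alive; and change scores can stay biased if dropout follows each subject's own decline.
- Note that Table 1C has no PRO row, so some questionnaires are missing for administrative reasons unrelated to health.

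The cost is SAP wording and modest programming on data already collected. The PRO analyses should remain labelled descriptive and supportive.

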9.7. Patient-reported Outcomes

9.7.1. FACT-Leu

The FACT-Leu, a self-administered PRO measure, will be used in this study. It will enable the evaluation of a subject's perceptions of health-related quality of life.

The FACT-Leu is a 44-item, self-reported leukemia-specific measure that is used to quantitatively assess an individual's perception of how the disease affects their day-to-day life. It includes 5 subscales, ie, physical well-being, social/family well-being, emotional well-being, functional well-being, and leukemia-specific concerns. All FACT-Leu subscale and aggregated scores showed high internal consistency and high test-retested reliability.⁴ A sample of the FACT-Leu containing representative questions is provided in [Attachment 1](#).

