Attachment 1: Sample FACT-Leu (Version 4)

Below is a list of statements that other people with your illness have said are important. **Please circle or mark one number per line to indicate your response as it applies to the past 7 days.**

		PHYSICAL WELL-BEING	Not at all	A little bit	Some-what	Quite a bit	Very much
GP	1	I have a lack of energy	0	1	2	3	4
GP	2	I have nausea	0	1	2	3	4
GP	3	Because of my physical condition, I have trouble meeting the needs of my family.....	0	1	2	3	4
GP	4	I have pain	0	1	2	3	4
GP	5	I am bothered by side effects of treatment	0	1	2	3	4
GP	6	I feel ill	0	1	2	3	4
GP	7	I am forced to spend time in bed	0	1	2	3	4

		SOCIAL/FAMILY WELL-BEING	Not at all	A little bit	Some-what	Quite a bit	Very much
GS	1	I feel close to my friends.....	0	1	2	3	4
GS	2	I get emotional support from my family	0	1	2	3	4
GS	3	I get support from my friends	0	1	2	3	4
GS	4	My family has accepted my illness	0	1	2	3	4
GS	5	I am satisfied with family communication about my illness	0	1	2	3	4
GS	6	I feel close to my partner (or the person who is my main support)	0	1	2	3	4
Q1		Regardless of your current level of sexual activity, please answer the following question. If you prefer not to answer it, please mark this box and go to the next section.					
GS	7	I am satisfied with my sex life 	0	1	2	3	4

Please circle or mark one number per line to indicate your response as it applies to the past 7 days.

EMOTIONAL WELL-BEING

		No t at all	A little bit	Some- what	Quit e a bit	Very muc h
GE 1	I feel sad	0	1	2	3	4
GE 2	I am satisfied with how I am coping with my illness.....	0	1	2	3	4
GE 3	I am losing hope in the fight against my illness.....	0	1	2	3	4
GE 4	I feel nervous.....	0	1	2	3	4
GE 5	I worry about dying.....	0	1	2	3	4
GE 6	I worry that my condition will get worse.....	0	1	2	3	4

FUNCTIONAL WELL-BEING

		Not at all	A little bit	Some -what	Quite a bit	Very muc h
GF1	I am able to work (include work at home).....	0	1	2	3	4
GF2	My work (include work at home) is fulfilling	0	1	2	3	4
GF3	I am able to enjoy life	0	1	2	3	4
GF4	I have accepted my illness	0	1	2	3	4
GF5	I am sleeping well	0	1	2	3	4
GF6	I am enjoying the things I usually do for fun.....	0	1	2	3	4
GF7	I am content with the quality of my life right now.....	0	1	2	3	4

Please circle or mark one number per line to indicate your response as it applies to the past 7 days.

ADDITIONAL CONCERNS		Not at all	A little bit	Some- what	Quite a bit	Very much

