5.11. Patient-Reported Outcomes

5.11.1. FACT-Leu

The FACT-Leu is a 44-item² self-reported measure used to quantitatively assess individuals' perception of how the disease affects their daily life. It includes 5 subscales, ie, physical well-being (PWB), social/family well-being (SWB), emotional well-being (EWB), functional well-being (FWB), and leukemia-specific concerns (LeuS). All FACT-Leu subscales and aggregated scores showed high internal consistency and high test-retested reliability.

The FACT-G is considered appropriate for use with subjects with any form of cancer, and has also been used and validated in other chronic illness conditions. The additional items of the FACT-Leu and LeuS allow for constructing a leukemia subscale. The subject is asked to rate the scale items as it applies to the past 7 days, on a 5-point scale (0=not at all, 1=a little bit, 2=somewhat, 3=quite a bit, 4=very much). Negatively stated items will be reversed by subtracting the response from 4. After reversing the proper items, items are summed to a total to generate a score on a (sub) scale^{3,4}.

- FACT-Leu trial outcome index (TOI) = PWB + FWB + LeuS
- FACT-G total score = PWB + SWB + EWB + FWB
- FACT-Leu total score = PWB + SWB + EWB + FWB + LeuS

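### As written, the FACT-Leu scoring rules count each skipped item in a scored subscale as 0, the worst value, because no proration is stated

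*SAP*

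**What the plan says.** SAP 5.11.1 gives the only scoring formula. Items are rated 0 to 4. "Negatively stated items will be reversed by subtracting the response from 4", and then: "After reversing the proper items, items are summed to a total to generate a score on a (sub) scale". Two references on the FACT system are cited at that sentence. The composite scores are simple sums of subscales, for example "FACT-Leu total score = PWB + SWB + EWB + FWB + LeuS". The trial outcome index (TOI) adds the physical (PWB), functional (FWB) and leukemia (LeuS) subscales.

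SAP 6.7.2.7 gives the only rule for missing items. For a subscale to be computed, "there must be >50% non-missing items; otherwise the respective subscale score is considered missing", and any composite containing a missing subscale is also missing. Nothing is said about the unanswered items in a subscale that passes the threshold. Protocol 9.7.1 and 11.10 add nothing on this.

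The form in Protocol Attachment 1 expects some missing items. Above the sex-life item (GS7, in the social/family subscale, SWB) it tells the subject: "If you prefer not to answer it, please mark this box and go to the next section".

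The planned analysis in SAP 6.7.2.7 is descriptive, by arm and time point, for nine measures. Seven are FACT-Leu scores (five subscales, TOI and total).

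**The concern.** The two rules do not fit together. One permits scoring an incomplete subscale; the other supplies only a plain sum. Adding up the answered items gives the same result as entering 0 for each blank. After reversal, 0 is the least favorable answer on every item, so blanks pull the score toward poor quality of life.

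At stake is whether the FACT-Leu summaries can be read as quality of life or as a mixture of quality of life and form completion. The planned outputs would not reveal the difference, because the compliance rate in SAP 6.7.2.7 counts questionnaires received, not items answered. A returned but partly blank form counts as compliant while its score is lowered.

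**Working it through.** **Inputs.** Item counts come from Protocol Attachment 1: PWB 7, SWB 7, emotional (EWB) 6, FWB 7, LeuS 17. The item range of 0 to 4 and the sum rule come from SAP 5.11.1; the threshold of more than 50% comes from SAP 6.7.2.7.

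**Plan's own figure.** Protocol 9.7.1 states: "The FACT-Leu is a 44-item, self-reported leukemia-specific measure". The count is 7 + 7 + 6 + 7 + 17 = 44, which agrees.

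**What the rules imply.** There are two literal readings of a sum with a blank in it. Either the sum is missing, or the blank contributes nothing. The first would make every incomplete subscale missing and leave the 50% threshold with no purpose. That leaves the second, in which a blank counts as 0.

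**Formulas.** For a subscale of n items with a answered:
- plain score = sum of answered items
- prorated score = (sum of answered items) × n / a
- plain / prorated = a / n
- fewest answers allowed = floor(n/2) + 1

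| Subscale | n | Fewest answered | Most missing | Plain / prorated | Highest possible plain sum at that point |
|---|---|---|---|---|---|
| PWB, SWB, FWB | 7 | 4 | 3 (43%) | 4/7 = 57% | 16 of 28 |
| EWB | 6 | 4 | 2 (33%) | 4/6 = 67% | 16 of 24 |
| LeuS | 17 | 9 | 8 (47%) | 9/17 = 53% | 36 of 68 |

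The ratios need no assumption about the answers. Points lost do. If answered items average v, the loss is v × (items missing). For v from 2 to 4 (an assumption), the loss at the fewest answers allowed is 6 to 12 points on a 7-item subscale, 4 to 8 on EWB and 16 to 32 on LeuS. With v = 3 and all five subscales at the limit, 3 + 3 + 2 + 3 + 8 = 19 items are missing. The total score is then 3 × 25 = 75 instead of 3 × 44 = 132.

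**Optional item only.** With six of seven SWB items answered, plain / prorated = 6/7, a loss of one seventh (14%). If the other six items are all at 1, 2, 3 or 4, the plain sum is 6, 12, 18 or 24 against 7, 14, 21 or 28, a loss of 1 to 4 points. The loss passes in full into the FACT-Leu total score. TOI does not contain SWB, so it is unaffected.

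**Effect on a group mean.** If a share q of subjects skips only GS7 and the item mean is v, mean SWB falls by q × v. The documents give neither figure. Assuming q = 10%, 30% or 50% and v = 2 to 3, the fall is 0.2 to 0.3, 0.6 to 0.9, or 1.0 to 1.5 points out of 28.

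**The case against.** The strongest reply is that the SAP nowhere says in words that a missing item is set to 0. It says how items combine and when a subscale may be computed, and it cites two FACT publications at the summing sentence. If those sources prorate and were meant to govern, the programmed scores could be correct. This stands in part. The content of the references cannot be checked from the documents, so the point is limited to what the SAP's own text produces. But the SAP does not say that it adopts a missing-item rule from them. A programmer following it literally would sum the answered items.

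The second reply concerns impact, and most of it stands. The PRO endpoints are secondary and descriptive. No test, model or change-from-baseline analysis is planned for them, whereas SAP 6.8.2 and 6.8.4 name change from baseline for laboratory values and vital signs. The large losses in the table apply only to subjects at the exact minimum number of answers, and nothing shows how many there would be. Protocol Table 1C, for the period during Amendment 6, lists no PRO collection.

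A reader might infer more than the documents support:
- **That the comparison between arms is biased.** This requires skipping to differ by arm. The documents do not show that it does, nor that sicker subjects skip more. With similar skipping and similar answers in both arms, the shift would be similar and the contrast little changed.
- **That almost half of any subscale can be blank.** This fits LeuS (47%) and the 7-item subscales (43%), but not EWB, where the limit is one third.
- **That the optional item depresses every composite.** It cannot touch TOI.

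**Conclusion.** The concern holds for the text as written. SAP 5.11.1 and 6.7.2.7 together make each skipped item in a scored subscale count as 0. The resulting score is below its prorated value unless every answered item is also 0, and below what full answers would have given unless the skipped items would truly have scored 0. The extreme is 57%, 67% or 53% of the prorated score, depending on the subscale. The one source of blanks that the form itself invites costs one seventh of SWB and carries into the total score.

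The conclusion rests on the SAP's own formula and on the 50% threshold having a purpose; it would change only if the cited references govern scoring and prorate. The consequence is confined to the seven FACT-Leu summaries. Complete response, overall survival, the alpha allocation and the stopping decision do not depend on them.

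**What to change.** In SAP 5.11.1 and 6.7.2.7, state that when more than 50% of a subscale's items are answered, its score is (sum of answered items after reversal) × (number of items in the subscale) / (number answered), and that TOI and the total scores are computed from these prorated subscales. If the cited references were meant to supply the rule, the formula should still be written out, so that two programmers obtain the same score from the same form.

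The cost is one sentence in the SAP and one line of code. No further data are needed, because the rule uses the item responses already recorded. Proration carries its own assumption, that a skipped item resembles the subject's other answers in that subscale, but this is more defensible than treating a blank as the worst answer.
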